11.1. Potential Risks

Medtronic follows rigorous Quality Assurance and Control procedures throughout the life of a product, from the business analysis phase through development, market release, and post-market surveillance. A summary of the risk analysis and risk assessment specific to this study is included in the corresponding Micra IDE study Investigator Brochure or Report of Priors.

Potential risks and side effects associated with a device implant and follow up procedures are documented in the product labeling.

Table 10 provides a listing of potential Micra AEs and is not intended to be a comprehensive listing of all reportable Adverse Events. This listing is provided to facilitate more complete and consistent event reporting.

Table 10: Potential Micra system related Adverse Events included but are not limited to:

air embolism	myocardial damage
aneurysm or pseudoaneurysm	nerve damage
bleeding or hematoma	nerve or extracardiac stimulation
cardiac or vascular trauma	oversensing, undersensing, or loss of pacing therapy
device dislodgment or migration	pacemaker syndrome
device embolization	pain at access site or chest
endocarditis	pericarditis, pericardial effusion, or pericardial rub
fluid accumulation	peripheral ischemia
heart, vessel, or valve tissue damage	reduced device longevity
impaired cardiac function due to device	tissue necrosis such as myocardial infarction
incision site complication	threshold elevation
incision site infection or other infection	thrombus which may result in embolism, such as DVT, PE, or CVA
induction or acceleration of arrhythmias	toxic/allergic reactions
ineffective rate response	venous occlusion

Confidential

11.2. Potential Benefits

The potential benefits of the Micra implantable device are consistent with the bradycardia therapy provided by similar currently approved single chamber pacemakers. Patients experiencing untreated bradycardia may get an inadequate supply of oxygen to their brain or other organs. This may result in debilitating symptoms, including syncope, weakness, fatigue, shortness of breath, chest pains, and confusion or memory problems. Pacemakers remain the only known, long term effective treatment for bradycardia.⁵

In addition to the standard benefits which apply to all pacemakers for bradycardia, there may be additional benefits specific to the Micra system due to its design. With no device pocket, risk of infection, vascular complications and device pocket complications (hematoma, erosion, pain) may be reduced or eliminated. Pacing leads are currently regarded as the weakest link in the implanted system as they can lead to lead failure and system reliability issues lead fracture and lead insulation defects. There is no similar technology available to deliver pacing therapy without a lead. Therefore, possible additional benefits specific to the Micra system include:

- Avoid certain complications associated with traditional pacemakers due to Micra design:
 - Subclavian access complications (pneumothorax, occlusion)
 - Pocket complications (Hematoma, Erosion, infections)
 - Lead complications (dislodgement, fracture, infections, connection errors, interaction with vasculature & heart structures, extraction complications)
- Satisfy patient preferences:
 - Cosmetic appeal (lack of pocket)
 - Minimally invasive approach
 - Avoid pain and discomfort associated with pocket
- Efficiency:
 - Faster procedural time
- Increased Access to Brady Therapy
 - More patients have access to pacing therapy since Micra implant isn't limited by number of available specialists in emerging markets

The information gained from this study could result in the improved management of patients with the Micra system. Additionally, information collected from this study may assist in the design of new product(s)/therapy(ies) and/or instructions for use.

It is possible that the Micra Transcatheter Pacing System may offer no benefit.

⁵ Lancet 2004; 364: 1701–19

Confidential

11.3. Risk-Benefit Rationale

Initial study results from the global human study indicate the device is safe and effective for the intended use. Any potential risks associated with study participation are further minimized by selecting qualified investigators and study training. In addition, investigators will be actively involved in the implantation and follow-up of the subjects implanted with the investigational device/system. During the course of the study, risks will be continuously monitored, assessed and documented by the investigators. It is the investigator's decision to assess whether or not to continue the study at the respective site, should safety-related concerns arise.

Risks will be minimized by careful assessment of each subject prior to, during, and after implant of the investigational device which is the subject of the study. After implantation, subjects enrolled in a study are followed at regular intervals to monitor subject and device status. At each required follow-up, the device will be interrogated to verify appropriate function and to evaluate pacing, sensing, and defibrillation characteristics (as appropriate) and to assess any adverse events.

Medtronic has further minimized the possibility of risks by: performing required laboratory and pre-clinical testing prior to conducting human clinical studies, implementing quality control measures into production processes, providing guidelines for subject selection and evaluation, and providing adequate instructions and labeling.

Unavoidable Adverse Event Related to the Implant Procedure: An Adverse Event inherent to a surgical procedure that is expected to occur in all subjects for a projected duration including but not limited to:

Table 11: Unavoidable Adverse Events

Event Description	Time Frame (hrs) from end of Procedure
Anesthesia related nausea / vomiting	24 hrs
Low-grade fever (<100°F or < 37.8°C)	48 hrs
Pocket site / incisional pain	72 hrs
Mild to moderate bruising / ecchymosis	168 hrs (7 days)
Sleep problems (insomnia)	72 hrs
Back pain related to laying on the table	72 hrs

12. Adverse Event Assessments

12.1. Definitions/Classifications

Note: if the definition indicates "device", it refers to any medical device. This might be the device under investigation or any market released component of a system.

Confidential

Table 12: Adverse Event Definitions

Event Type	Definition⁶
Adverse Event (AE)	
Any untoward medical occurrence, unintended disease or injury, or untoward clinical signs (including abnormal laboratory findings) in subjects, users or other persons, whether or not related to the investigational medical device.
 
NOTE 1: This definition includes events related to the investigational medical device or the comparator.
 
NOTE 2: This definition includes events related to the procedures involved.
 
NOTE 3: For users or other persons, this definition is restricted to events related to investigational medical devices.
 
(ISO 14155:2011 section 3.2)

	
The medical events with disadvantages occurred during the clinical trials, no matter whether they are related to investigational medical devices or not.
 
(CFDA Order No.25 Article 93)

Serious Adverse Event (SAE)	
Adverse event that
 
 a) led to death, b) led to serious deterioration in the health of the subject, that either resulted in 
 1) a life-threatening illness or injury, or 2) a permanent impairment of a body structure or a body function, or 3) in-patient or prolonged hospitalization, or 4) medical or surgical intervention to prevent life-threatening illness or injury or permanent impairment to a body structure or a body function, c) led to fetal distress, fetal death or a congenital abnormality or birth defect. 
NOTE: Planned hospitalization for a pre-existing condition, or a procedure required by the CIP, without serious deterioration in health, is not considered a serious adverse event.
 
(ISO 14155:2011 section 3.37)

	
Any untoward medical occurrence during the clinical trial: results in death or serious deterioration in health; life-threatening diseases or injuries; causing

⁶ International Standard ISO 14155:2011(E). Clinical investigation of medical devices for human subjects – Good Clinical Practice.

Confidential

Event Type	Definition ⁶
	
permanent damage to the body structure or function; requires hospitalization or prolongation of hospitalization; requires medical operations or intervention for preventing from persistent or significant disability/incapacity; results in fetal distress, fetal death, or congenital anomaly/birth defect.
 
(CFDA Order No.25 Article 93)

Adverse Device Effect (ADE)	
Adverse event related to the use of an investigational medical device.
 
NOTE 1: This definition includes adverse events resulting from insufficient or inadequate instructions for use, deployment, implantation, installation, or operation, or any malfunction of the investigational medical device.
 
NOTE 2: This definition includes any event resulting from use error or from intentional misuse of the investigational medical device.
 
(ISO 14155:2011 section 3.1)

Serious Adverse Device Effect (SADE)	
Adverse device effect that has resulted in any of the consequences characteristic of a serious adverse event.
 
(ISO 14155:2011 section 3.36)

Unanticipated Serious Adverse Device Effect (USADE)	
Serious adverse device effect which by its nature, incidence, severity or outcome has not been identified in the current version of the risk analysis report.
 
NOTE: Anticipated serious adverse device effect (ASADE) is an effect, which by its nature, incidence, severity or outcome has been identified in the risk analysis report.
 
(ISO 14155:2011 section 3.42)

Device Deficiency	
Inadequacy of a medical device with respect to its identity, quality, durability, reliability, safety or performance.
 
NOTE: Device deficiencies include malfunctions, use errors, and inadequate labeling.
 
(ISO 14155:2011 section 3.15)

	
Any unreasonable risk caused by a medical device in normal use during clinical trial that may endanger human health or life safety, such as label error, quality issues, malfunction and etc.
 
(CFDA Order No.25 Article 93)

12.1.1. Relatedness

Procedure-Related: An event that is directly related to the implantation or modification procedure of a device/system.

System-Related: An Adverse Event that results from the presence or performance (intended or otherwise) of the device (e.g. Micra device, delivery catheter, or software).

Confidential

Micra Implantable Device Related: An adverse event that results from the presence or performance (intended or otherwise) of the Micra device

Delivery Catheter Related: An adverse event that results from the presence or performance (intended or otherwise) of the delivery catheter

Software Related: An adverse event that results from the performance (intended or otherwise) of the Micra software

Accessory / Tool Related

Programmer Related: An adverse event that results from the presence or performance (intended or otherwise) of the programmer

Introducer Related An adverse event that results from the presence or performance of the introducer

Implant Tool Related: An adverse event that results from the presence or performance of the implant tool (excluding delivery catheter and introducer)

Extraction Tool Related An adverse event that results from the presence or performance of the extraction tool

Note: If an event occurs as a result of a system component but it is unclear which component it is related to, the default will be to the last component used prior to the event being observed.

Hospitalization: An overnight hospital admission, where admission date and discharge date are different

An unsuccessful implant is not considered an adverse event; however any adverse events occurring during an unsuccessful implant attempt (e.g. dissection, perforation) must be recorded and classified.

12.1.2. Complication

Complication: An adverse event that results in death, involves any termination of significant device function or requires an invasive intervention.

Non-invasive when applied to a diagnostic device or procedure, means one that does not by design or intention:

- Penetrate or pierce the skin mucous membranes of the body, the ocular cavity or the urethra, or
 - Penetrate: to pass, extend, pierce, or diffuse into or through something; to enter overcoming resistance; to gain entrance to
 - Pierce: to force a way into or through something
- Enter the ear beyond the external auditory canal, the nose beyond the nares, the mouth beyond the pharynx, the anal canal beyond the rectum, or the vagina beyond the cervical os.

Blood sampling that involves simple venipuncture is considered noninvasive, and the use of surplus samples of body fluids or tissues that are left over from samples taken for non-investigational purposes is also considered noninvasive.

Major Complication:

A complication which results in:

- Death

Confidential

- Permanent loss of device function due to mechanical or electrical dysfunction of the device (i.e. pacing function disabled, leaving device abandoned electrically)
- System revision (explant, reposition, replacement)
- Hospitalization
- Prolonged Hospitalization by 48 hours or more

NOTE: Only system or procedure related AEs will be classified as a major complication, minor complication or an observation

Minor Complication: Any adverse event classified as a complication that is not a major complication (e.g. event classified as a complication solely based on intravenous drug administration)

Observation: Any adverse event that is not a complication.

12.1.3. Subject Death

All subject deaths must be reported by the investigator to Medtronic as soon as possible after the investigator first learns of the death. Document the adverse event that led to the subject death on an Adverse Event form. Further supporting evidence that is not originally provided by the site may be requested by Medtronic to aid in the adjudication of the death.

In the event of a subject death, the implanted system should be explanted and returned to Medtronic for analysis whenever possible. Prior to explant, the system should be interrogated and a full summary interrogation performed (save-to-media) when possible. If the system is not interrogated, an explanation must be documented. If any system component is returned to Medtronic, internal return product reporting systems may be used to gather additional information about the returned device/component.

A copy of the death certificate, if available and allowed by state/local law, should be sent to the Medtronic. When a death occurs in a hospital, a copy of the death summary report and all relevant hospital records should be sent to the Medtronic, if available. If an autopsy is conducted, the autopsy report should also be sent to the Medtronic if available and allowed by state/local law. When the death occurs at a remote site, it is the investigative site's responsibility to attempt retrieval of information about the death. Additionally, device disposition information should be updated. In summary, the following data will be collected:

Date of death

- Detailed description of death
- Cause of death
- Relatedness to system and/or procedure
- Device interrogation (if available)
- Device disposition information (if applicable)
- Death summary/hospital records (if available and allowed by local law)
- Autopsy report (if available and allowed by local law)
- Death certificate (if available and/or allowed by local law)

12.1.3.1. Death Classification and Reporting

Sufficient information will be required in order to properly classify the subject's death. The Investigator shall classify each subject death per the following definitions:

Confidential

Cardiac Death: A death directly related to the electrical or mechanical dysfunction of the heart.

Sudden Cardiac Death (SCD): Natural death due to cardiac causes, indicated by abrupt loss of consciousness within one hour of the onset of acute symptoms; preexisting heart disease may have been known to be present, but the time and mode of death are unexpected. If time of onset cannot be determined, SCD will alternatively be defined as any unexpected cardiac death occurring out of the hospital or in the emergency room as dead on arrival.

Non-sudden Cardiac Death: All cardiac deaths that are not classified as sudden deaths, including all cardiac deaths of hospitalized subjects on inotropic support.

Non-cardiac Death: A death not classified as a cardiac death.

Unknown: A death in which there is no clinical evidence to support:

- A direct relatedness to the system component or
- A probable cause relatedness to the system component or
- No relatedness to the system component

Regulatory reporting of Subject Deaths will be completed according to local regulatory requirements.

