14.1.6. Stopping Rule

No interim analysis is planned for this study. Therefore there is no stopping rule defined. The analysis will be conducted after data collection is completed, verified and locked.

14.1.7. Analysis Data Set, handling of missing data, non-compliance, error or non-reasonable data entry.

Statistical analysis procedures (procedures) will strictly comply to SOP of the Medical Research & Biometric Center, National Center for Cardiovascular Diseases. Please refer to other relevant documents for additional details.

Data entry error or non-reasonable values will be cleaned before data analysis. In the event of subject exit or withdrawal of consent, the subject will still be included in the final statistical analysis. The specific reasons for subject exit or withdrawal will be provided in detail in the statistical report. If no data can be collected from a subject during post-implant follow-up, additional sensitivity analysis may be performed.

This study will use the survival analysis method for the primary objective. Scenarios for censoring are previously defined. The Worst Case Scenario Analysis will only be performed if it is identified as a true missing (e.g. permanent missing of adverse event related data, and subsequently resulting in non-conclusive CEC review) or if the cause of death is unknown. The sensitivity analysis may count such missing data as failures.

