7.10.2 Deaths

Death information will be collected throughout the trial when the event occurs. Safety specialists will ensure that all deaths will be classified by the CEC. A summary table will be compiled with the death classification, as well as the relatedness to the procedure, system (including specific system component), accessory (including specific accessory or tool), and underlying condition or disease. The CEC classification of relatedness will be used. The number of events and percent of subjects will be provided.

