7.10.4.3 Death Classification

Sufficient information will be required in order to properly classify the subject's death. The investigator shall classify each subject death per the following definitions:

Cardiac death:

A death directly related to the electrical or mechanical dysfunction of the heart.

Sudden cardiac death (SCD):

Natural death due to cardiac causes, indicated by abrupt loss of consciousness within one hour of the onset of acute symptoms; preexisting heart disease may have been known to be present, but the time and mode of death are unexpected. If time of onset cannot be determined, SCD will alternatively be defined as any unexpected cardiac death occurring out of the hospital or in the emergency room as dead on arrival.

Non-sudden cardiac death:

All cardiac deaths that are not classified as sudden deaths, including all cardiac deaths of hospitalized subjects on inotropic support.

Non-cardiac death:

A death not classified as a cardiac death.

Unknown:

A death in which there is no clinical evidence to support:

- A direct relatedness to the system component or
- A probable cause relatedness to the system component or
- No relatedness to the system component

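### The death classes mix cause with device relatedness, so the death table can show an unexplained death as non-cardiac or place one death in two classes (minor; primary analysis unaffected)

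*Protocol*

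**What the plan says.** Protocol 12.1.3.1 sets the rule for the investigator: "The Investigator shall classify each subject death per the following definitions". A cardiac death is one directly related to electrical or mechanical dysfunction of the heart, with sudden and non-sudden subclasses. The other two classes are:

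- *Non-cardiac*: "Non-cardiac Death: A death not classified as a cardiac death".
- *Unknown*: "Unknown: A death in which there is no clinical evidence to support" any of three bullets. The first is "A direct relatedness to the system component or"; the other two concern probable relatedness and absence of relatedness to the system component.

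SAP 7.10.4.3 carries both over, with non-cardiac again worded as "A death not classified as a cardiac death".

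Relatedness also has its own place. Protocol 12.1.3 lists cause of death and relatedness to system or procedure as separate data items. SAP 7.10.2 reports them separately: "A summary table will be compiled with the death classification, as well as the relatedness to the procedure, system" and further categories.

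Protocol 13.1 has the Clinical Events Committee (CEC) review deaths against the applicable definitions and set the final classification. Protocol 14.1.7 allows the worst-case analysis of the primary endpoint for true missing data "or if the cause of death is unknown. The sensitivity analysis may count such missing data as failures". SAP 7.4 and 7.9.1.4 keep the true-missing trigger but do not list unknown cause of death. SAP 7.9.1.4 adds a sensitivity analysis that counts events of CEC-unknown relationship as failures.

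**The concern.** A three-way classification of death should answer one question: what did the subject die of? Here the first two classes answer that question and the third answers another, namely whether the evidence links the death to the device. This has two effects.

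First, the non-cardiac class requires no identified non-cardiac cause, so it takes in deaths that nobody could explain. For a device implanted in the heart, non-cardiac is the reassuring label, so any misplacement tends to flatter the safety table.

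Second, the cause axis has no unknown category. The only class with that name measures relatedness, which is already recorded and tabulated elsewhere. The words about unknown cause in Protocol 14.1.7 therefore have no class to point to.

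At stake are the descriptive death table in the study report and the clarity of one optional sensitivity trigger.

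**Working it through.** The plan gives no figure on this point to reproduce, so the check applies the definitions as written to each combination of cause and relatedness evidence.

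**Inputs.** The class definitions come from Protocol 12.1.3.1 and SAP 7.10.4.3. The three bullets under *unknown* are joined by *or*. I read them in the ordinary, kinder way: a death is unknown if there is no evidence for relatedness, for probable relatedness, or for its absence. No precedence rule is stated in either document.

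**Step 1: apply the definitions.**

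| Cause of death | Evidence on relatedness to a system component | Class or classes met as written |
|---|---|---|
| Cardiac | Some, either way | Cardiac |
| Cardiac | None | Cardiac and unknown |
| Identified non-cardiac | Some, either way | Non-cardiac |
| Identified non-cardiac | None | Non-cardiac and unknown |
| Not established | Some, either way | Non-cardiac |
| Not established | None | Non-cardiac and unknown |

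Of the six rows, two give a single class that matches the cause. Three give two classes. One, the fifth, gives a single class that does not match the cause.

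**Step 2: two example records.**

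- *Record A.* An unwitnessed death with no autopsy and no cause established, which the CEC judges unrelated to the system. A judgement of no relatedness means there is evidence on the third bullet, so the death is not unknown. It has not been classed cardiac, so it is non-cardiac. The fallback rule for sudden cardiac death does not rescue it, because that rule covers unexpected *cardiac* deaths and so presupposes a cardiac cause.
- *Record B.* A fatal stroke with no evidence either way on a device origin. The cause is known and non-cardiac, so it meets non-cardiac. There is no evidence on any of the three bullets, so it also meets unknown.

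**Step 3: trace where the class is used.**

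| Output | Does it use the death class? |
|---|---|
| Primary endpoint and pass/fail (Protocol 6.2.1, 14.1.1, 14.1.5; SAP 7.9.1) | No. It uses CEC-determined relatedness and major-complication status. |
| Sensitivity analysis for unknown relationship (SAP 7.9.1.4) | No. It uses the CEC relationship field. |
| Death summary table (SAP 7.10.2) | Yes, directly. |
| Worst-case trigger on unknown cause (Protocol 14.1.7) | Not stated. It refers to cause and cites no class. |
| Worst-case trigger in SAP 7.4 and 7.9.1.4 | No. Unknown cause is not listed. |

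The documented effect is therefore on the death table. The worst-case trigger has a gap in definition and a mismatch between Protocol and SAP, but no stated link to these classes.

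**Step 4: size.** The documents give no expected number of deaths, so no expected number of misplaced deaths can be calculated. Each affected death changes one entry in the table, which is 1/82 = 1.2% of the planned enrollment.

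**The case against.** The best defence is that the safeguards around these definitions matter more than the definitions. At least three physicians who are independent of the sponsor adjudicate device-related deaths, the CEC sets the final class, and the table prints relatedness beside the class. A careful committee would probably not call an unexplained death non-cardiac. This limits the harm but does not remove the defect: the committee works from the applicable definitions, and the documents give no others for death.

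A second defence is that Record A is contrived, because a normal device test need not count as evidence of no relatedness, and system relatedness also covers the delivery catheter and software. That is fair, and it is why Record A is stated as a death the CEC has *judged* unrelated. Without that judgement it meets both non-cardiac and unknown, which is still not a usable classification.

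A reader might go further and infer that Record A would be censored and never tested as a failure, or that Record B would wrongly be counted as one. The documents support neither. Protocol 14.1.7 turns on the cause of death, which is its own data item, and does not say that the trigger is read from the class in 12.1.3.1. Record B is the kind of case for which SAP 7.9.1.4 prescribes a failure count, so counting it follows the plan.

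A reader might also argue that one death can decide the worst-case result. With 82 subjects and no early censoring, the lower log-log limit is S^exp(1.96 × se), where S = 1 − d/82 and se = √(d/(82(82 − d))) / |ln S|. For d = 6, S = 0.9268 and the limit is 84.4%, above 83%. For d = 7, S = 0.9146 and the limit is 82.9%, below it. The arithmetic is right, but one event can tip any result at that boundary. Attributing it to these definitions needs an assumed number of unexplained deaths and a link to the class that the plan does not state.

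**Conclusion.** The definitions do not work as a classification. They combine cause and relatedness, they overlap without a precedence rule, and they leave no class for a death whose cause was not established. The demonstrable consequence is that the death table in SAP 7.10.2 can show an unexplained death as non-cardiac or place one death in two classes. This holds under the kinder reading of the bullets and assumes only that such a death occurs.

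The primary estimate, its confidence limit, the pass/fail rule and the sample size are untouched. The SAP's analysis of unknown relationship already covers deaths of undetermined relatedness. What it does not cover is a death of unknown cause judged unrelated. For such a death Protocol 14.1.7 offers a worst-case route without a matching class, and the SAP does not list the trigger.

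Severity: minor. It is a wording defect in a descriptive safety output, with an undefined term in an optional sensitivity analysis.

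**What to change.** In Protocol 12.1.3.1 and SAP 7.10.4.3, define the classes by cause and make them exclusive:

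- *Cardiac*: as now.
- *Non-cardiac*: a death with an identified non-cardiac cause.
- *Unknown*: a death for which the available information does not allow the CEC to assign a cardiac or a non-cardiac cause.

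Remove the three relatedness bullets from *unknown*, and keep relatedness only in the separate field that SAP 7.10.2 already tabulates.

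Then use the CEC's unknown-cause class as the trigger in Protocol 14.1.7, and add the same trigger to SAP 7.4 and 7.9.1.4. Rewording the classes alone would not bring any death into the SAP's worst-case analysis, so both steps are needed.

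The cost is a few lines in each document and a matching edit to the adjudication form. No new data are needed and enrollment stays at 82. The downside is that a few deaths may move from non-cardiac to unknown, which looks slightly less favourable.
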